InControl Medical created a line of products FDA approved for urinary incontinence and fecal incontinence (10). These devices are non-implanted, customizable, battery-operated vaginal probes made of medical grade silicon and provide electrical stimulation to the pelvic floor. One of the devices, ApexMTM provides electrical stimulation at frequencies alternating between 13 Hz and 50 Hz and allows the clinician to adjust the intensity as well as the duration of the electrical stimulation. We propose the use of low power electrical stimulation for the treatment of pain in patients diagnosed with CPP. We will deliver the electrical stimulation using ApexMTM, adjusting the power to a sensory threshold to prevent muscle contraction.

Primary goal:

To evaluate the use of a domiciliary intravaginal, non- implanted electrical stimulation device in the treatment of chronic pelvic pain. Hypothesis: ES will decrease pain as measured by the visual analog scale and brief pain inventory (18).

Secondary goals:

To evaluate the effect of ES on overall quality of life. Hypothesis: ES will improve quality of life as measured by the Short Form-36. (16)

To evaluate the effect of ES on sexual function. Hypothesis: ES will improve sexual functioning as measured by Female Sexual Function Index (17)

To evaluate the use of ES on use of pain medications. Hypothesis: ES will decrease dosage and frequency of pain medication use. This will be measured by use of a daily pain medication journal. Patients will complete a journal listing the type, amount and dosage of pain medications used on a daily basis.

SIGNIFICANCE

If a positive effect is seen, a personal vaginal device designed for home use can be offered to patients with chronic pelvic pain. Patients would be able to take pelvic floor rehabilitation from the physical therapy office into their home. Furthermore, it would justify a larger, multi-center, randomized Version 6 Aug 2015

controlled trial comparing the ApexMTM device to standard in office physical therapy.

STUDY DESIGN

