Our study is a prospective, randomized controlled trial in patients diagnosed with chronic pelvic pain. To make the diagnosis, patients must have non-cyclic pelvic pain for duration greater than 6 months which results in functional disability. This is defined as patient reported limitations in social or occupational functioning. One physician will make the diagnosis from patients evaluated in one treatment facility. Inclusion criteria: women >/= 18 years old who are sexually active or desire to be sexually active, no active infection, diagnosed with non-cyclic chronic pelvic pain, duration of symptoms greater than 6 months, neurologically intact, able to accommodate and tolerate the device, not pregnant and not attempting to achieve pregnancy. Exclusion criteria include pregnancy, currently active in pelvic floor physical therapy, active malignancy, patients unable to contract their pelvic floor secondary to causes such as myelopathy, spinal cord trauma, patients with diabetes, vestibulodynia, vulvodynia, a pacemaker, defibrillator or other implanted neuro-modulatory devices, patients with a hypotonic pelvic floor, or those currently on treatment for pain with topical lidocaine, gabapentin or other medications or injections outside of standard analgesics, and severe psychiatric disorders. We will instruct patients to avoid starting any new medications for the treatment of their pelvic pain during the trial.

We will invite subjects meeting criteria to participate in the study. If subjects are interested, they will review and sign the informed consent. Randomization is based on age, diagnosis, and duration of symptoms. Researchers will collect the patient's demographics and general medical history at the initial visit. This includes relevant past medical history, surgical history, allergies, medicines, and social history. At each visit, we will assess pain, quality of life and sexual function. Pain is assessed using the visual analog scale, quality of life measured by the SF-36, sexual dysfunction measured by the female sexual function and pain medication use by a daily journal. We ask each subject to record the date, each completed session, as well as pain medication usage in a provided daily journal. We will make these assessments at baseline, 4 weeks, 8 weeks and 12 weeks.

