The ApexM device has a built-in feature to measure compliance. Using the device keypad, the clinician can activate the compliance tracker which utilizes a series of lights. Each illuminated light accounts for the completion of six ApexM sessions. The clinician can also reset and clear the compliance tracker. At each follow-up visit, after documenting the number of illuminated lights, we will reset the compliance tracker in order to record compliance for the following four weeks. Only the clinician will have the code to activate and reset the compliance tracker. If the subjects are compliant, four illuminated lights should appear at each follow-up visit. Both the original and sham device is equipped with the compliance feature. Additionally, subjects will complete a daily journal documenting each session over the course of 12 weeks. Chronic pelvic pain patients suffer from persistent and refractory pain and generally are very motivated to comply with therapy. Barriers to compliance with standard in-office pelvic floor physical therapy are addressed by offering a personal device utilized at home.

During the study, we ask that all subjects refrain from starting other treatment modalities except standard analgesics including acetaminophen or NSAIDs for the 12 weeks. This includes hormonal therapies, new oral or topical medications, pelvic floor physical therapy, and psychotherapy.

DATA ANALYSIS

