We will record demographics, general medical information, questionnaires, and medication usage (including frequency and doses) using the REDCap database designed by the researcher and hosted by the Cleveland Clinic. REDCap (Research Electronic Data Capture) is a secure, web- based application designed to support data capture for research studies, providing 1) an intuitive interface for validated data entry; 2) audit trails for tracking data manipulation and export procedures; 3) automated export procedures for seamless data downloads to common statistical packages; and 4) procedures for importing data from external sources. The database will be reviewed by a statistician prior to data collection. Only the PI and research co-investigators will have access to the stored information. Only the PI, co-PI's and those responsible for analysis will have rights to export identifiable data. The subject's personal health information will be stored in the secure research database and only limited research personnel have access to this database. Great care will be taken to ensure that confidential health information is stored securely and accessible only to the PI and co-investigators.

RANDOMIZATION

In order to minimize bias in the study, we will stratify subjects based on presence or absence of levator spasm.

STATISTICAL METHODS

Numerical values will summarized by mean and standard deviation when they appear to have a normal distribution; otherwise, they will be summarized by median and interquartile range. Categorical values will be summarized by frequency and percentage. Univariable comparisons between groups will be made using two sample t-tests, Wilcoxon rank sum tests, or Chi-square tests, depending on the level of measurement and data distributions.

STUDY AIM ANALYSIS

- 1. Change in pain score from baseline to 12 weeks will be compared using a two-sample t-test. A multivariable linear regression model may be considered if baseline differences between groups are observed.
- 2. Changes in SF-36 subscores from baseline to 12 weeks will be compared using Wilcoxon rank sum tests.
- 3. Changes in FSFI subscales from baseline to 12 weeks will be compared using Wilcoxon rank

sum tests.

4. Frequency of medication from baseline to 12 weeks may be compared using a poison regression model. Dose of medication will be compared using a Wilcoxon's rank sum test.

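### The medication-dose comparison has no defined dose variable: one rank test across different analgesics, with no common unit, no per-drug analysis and no baseline term

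*Combined protocol and SAP*

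**What the plan says.** Lower medication use is a named secondary hypothesis (Secondary goals): "ES will decrease dosage and frequency of pain medication use". The data come from a daily diary: "Patients will complete a journal listing the type, amount and dosage of pain medications used on a daily basis".

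Study Aim Analysis item 4 has two sentences. On frequency: "Frequency of medication from baseline to 12 weeks may be compared using a poison regression model" (plainly Poisson regression). On dose: "Dose of medication will be compared using a Wilcoxon's rank sum test".

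Three statements in Study Design bear on which drugs women may take:
- Entry excludes those treated with certain named drugs or "other medications or injections outside of standard analgesics", so standard analgesics are allowed at entry.
- "We will instruct patients to avoid starting any new medications for the treatment of their pelvic pain during the trial".
- Other treatments are not to be started, "except standard analgesics including acetaminophen or NSAIDs for the 12 weeks".

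**The concern.** A rank sum test needs one ordered number per woman. Item 4 does not say what that number is. It gives no unit, no conversion between drugs, no analysis by drug or class, and no rule for women who take several drugs or change drug. Items 1 to 3 all compare change from baseline to 12 weeks. The dose sentence does not say whether week-12 dose or change is ranked; the reference to baseline stands only in the frequency sentence.

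If amounts of different drugs are ranked together, a woman's rank depends partly on which drug she takes. A woman who changes drug can show a large change in amount with no change in how often she needs relief. At stake is the dosage half of the medication aim: a real reduction could be missed, or an apparent one misread. An undefined variable also leaves several defensible dose measures to choose from once results are known.

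**Working it through.** The plan states no effect size, SD or power for medication dose, so there is no figure to reproduce. The text settles whether the variable is defined; arithmetic can only illustrate the consequences.

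**1. Can women be on different drugs, or change drug?** The permitted group names acetaminophen and NSAIDs, which is more than one class, and the diary has a field for type. One Study Design statement discourages new pelvic pain medication; a later one exempts standard analgesics. Changes between permitted drugs are therefore discouraged but possible. The actual mix and rate of change are not given.

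**2. What a change of drug does to milligrams.** Assumed tablet strengths are 500 mg and 200 mg. Two tablets a day of the first is 2 × 500 = 1000 mg; two of the second is 2 × 200 = 400 mg. The apparent change is (400 − 1000)/1000 = −60%, with the tablet count unchanged.

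**3. Power.** From the documents: 46/2 = 23 per arm (the Power Analysis figure for pain, borrowed here) and two-sided 0.05. Assumed:
- strengths of 500, 200 and 220 mg in a 40/40/20 mix
- gamma-distributed baseline tablet use (shape 2 or 4)
- log-SD 0.4 for individual change
- sham change −5%, true active-arm reduction 30%
- the same proportion in each arm re-drawing a drug from the mix

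Re-drawing can return the same drug with probability 0.4² + 0.4² + 0.2² = 0.36, so 20% re-drawing means 0.20 × 0.64 = 12.8% actually changing.

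Simulated power (2,000 to 4,000 trials per setting), ranking change from baseline:

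| Re-drawing drug | Milligrams | Common unit | Gain |
|---|---|---|---|
| none | 53% | 55% | 2 points |
| 5% | 53% | 57% | 4 points |
| 20% | 40% | 51% | 11 points |

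Other runs at 20% re-drawing, varying the baseline distribution, gave 45% against 55–57% and 48% against 61%, so the gain is roughly 10 to 13 points.

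If the unadjusted week-12 dose is ranked, power is about 15–20%, against about 61–63% for a common unit with baseline adjustment. Most of that gap is the baseline: in milligrams, with no drug changes and gamma shape 2, power is 18% ranking week-12 dose and 54% ranking change, a difference of 36 points from that choice alone. On the week-12 reading the drug mix also costs power without any switching: with a 40% reduction and gamma shape 4, 45% in milligrams against 61% in a common unit.

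**4. Type I error.** A second illustration has two drugs, 1000 mg per unit for one and 200 to 500 mg for the other, and no true change in units taken. The share of trials significant when change in milligrams is ranked:

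| Switching to the lower-mg drug, active vs sham | Significant |
|---|---|
| none, or 30% vs 30% | about 5% |
| 30% vs 10% | about 12% |
| 30% vs 0% | about 21% |

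The unit-scaled test stays at about 5% throughout.

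**The case against.** The strongest reply is that the plan is incomplete rather than wrong. It never says that raw milligrams are ranked, and a reader who infers this goes beyond the text. That stands: the supported defect is an undefined dose variable, with pooling across drugs implied by a single test.

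A reader might also infer that differences between drugs swamp the effect. The figures do not support that when change is ranked: a stable mix of drugs costs about 2 points. The larger loss depends on a switching rate that no document gives, in a trial that tells women not to start new medication for pelvic pain.

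Nor do the documents support inferring a false-positive problem. Randomisation protects the test when drug mix and switching are alike in both arms; inflation requires switching that differs by arm, which is a further assumption.

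The simulation also leans towards the remedy, because the effect is generated in tablets and then tested in tablets. The proposed measure matches a tablet count only if each woman takes one drug at a time and the reference amounts are proportional to tablet strength.

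Finally, it would be wrong to infer that no baseline is planned. Study Design takes a medicines history at the initial visit and lists medication use by journal among the measures assessed at baseline. What is missing is a stated pre-treatment recording period and any use of baseline in the dose test.

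These replies limit the size of the problem. None of them supplies the missing definition.

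**Conclusion.** The concern holds as a gap in definition. Item 4 does not fix the unit, the handling of different drugs, the time window or the use of baseline, so the dosage hypothesis has no determinate test. Under the stated assumptions the unit alone is worth about 2 points of power with no drug changes and about 11 with 20% re-drawing, when change is ranked for a 30% reduction. The missing baseline term matters more: unadjusted week-12 dose gives about 15–20% power, against about 61–63% with a common unit and baseline adjustment. Type I error is near 5% if switching is equal between arms.

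The drug mix, switching rate, tablet strengths and variability are all assumed, so these figures show direction and order of size and are not predictions for this trial. The point concerns one part of a secondary goal and does not touch the primary pain comparison.

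**What to change.** Before unblinding, replace the dose sentence in item 4 with a definition:

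- **Variable.** For each drug, daily amount divided by a fixed analysis reference amount for that drug; sum over drugs; average over a fixed final window, for example weeks 9 to 12. The sum covers women who take several drugs or change drug.
- **Comparison.** Compare arms adjusting for the same measure at baseline, for example by rank ANCOVA.
- **Sensitivity.** Repeat by drug class.
- **Baseline.** Hand out the journal at consent where consent precedes the initial visit. The Consent section also lets a woman sign at that later visit, where randomisation takes place; for these women, use the medication history taken then, recorded with amount and dose.

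The two Study Design statements on starting new medication should also be reconciled, so that the analysis knows which changes of drug to expect.

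The cost is SAP wording, a short conversion table and earlier issue of the journal, which already records type, amount and dosage. The reference amounts are analysis conversions only and do not affect care. The downsides are small: they must be fixed in advance, and some baselines will rest on recall.

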Additional analyses using longitudinal methods, including linear mixed effects models and generalized linear mixed effects models, may be used in subsequent analyses to explore the length of time that elapses before the treatment benefit is observed. In all analyses, statistical significance will be determined by a p-value less than or equal to 0.05. Analyses will be performed using R version 3.1.1 (2014-07-10) statistical software (or a later version).

Two interim analyses are planned for this study, to be conducted at 25% recruitment and 50% recruitment. These analyses will be conducted using significance levels of 0.017 and 0.033, respectively. A stopping rule will be applied of any statistically significant increase in pain from baseline as reported on the visual analog scale. The percentage of patients dropping out from the study will also be monitored, with a significantly higher percentage of electrical stimulation patients dropping out being considered a potential safety issue.

POWER ANALYSIS

The researcher currently estimates typical reported pain from this population of patients to be between 8 and 9 on a 10 point scale. A clinically meaningful improvement would be a 30% reduction in reported pain. For the purposes of the power analysis, we assume that the placebo effect of the sham treatment may reduce reported pain by 10%. We assign the mean baseline pain value of 8.5 to each group with a standard deviation of 1. A 30% reduction in pain corresponds to a mean score of 5.9 and a 10% reduction of pain corresponds to a mean score of 7.7. The sample size analysis is based on a two-sample, two-sided t-test with a significance level of 0.05 and 80% power. The sample size analysis indicates that for a 30% reduction in pain, a total sample size of 46 is required to provide 80% power for the study. To reduce the impact of attrition on the final study results, we plan on recruiting 10% more than the minimum sample size. This amounts to a total of 52 patients (26 patients per arm).

ADVERSE EVENTS AND DATA SAFETY MONITOR

Patients are asked to record any side effects, adverse effects and unanticipated problems daily. In Version 6 Aug 2015

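### No score or rule decides the SF-36 and FSFI hypotheses; reading any one significant subscale as support raises the false-benefit chance to about 7-18% per instrument

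*Combined protocol and SAP*

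**What the plan says.** Under Secondary goals, the protocol gives one hypothesis per instrument. For quality of life: "Hypothesis: ES will improve quality of life as measured by the Short Form-36". For sexual function: "Hypothesis: ES will improve sexual functioning as measured by Female Sexual Function Index". Each is tied to the instrument as a whole, and no score within it is singled out.

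Study Aim Analysis then turns each hypothesis into several tests. Item 2: "Changes in SF-36 subscores from baseline to 12 weeks will be compared using Wilcoxon rank sum tests". Item 3: "Changes in FSFI subscales from baseline to 12 weeks will be compared using Wilcoxon rank" (the sentence ends by completing the name of the rank sum test). After the four items, one threshold is set for everything: "In all analyses, statistical significance will be determined by a p-value less than or equal to 0.05".

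The only other significance levels in the document, 0.017 and 0.033, belong to the two interim analyses. Nowhere is there a total or summary score, a lead subscale, a testing order, a multiplicity adjustment or a rule that converts a set of subscale results into an answer on quality of life or sexual function.

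**The concern.** The number of hypotheses does not match the number of tests. Suppose one SF-36 subscore gives p = 0.04, and the rest show nothing or lean the other way. The plan calls that subscore significant but does not say whether quality of life improved. This gap exists whatever the number of subscales or their correlation.

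It also leaves the choice of headline until the results are known. If the report treats any significant subscale as support for the instrument's hypothesis, the chance of a false claim of benefit exceeds that of a single test. The Significance section links further use of the device, and a larger trial, to a positive effect that it does not define. A chance subscale finding could therefore be cited in support.

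**Working it through.** The plan states no error rate for these two hypotheses, so there is no figure of its own to reproduce.

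**Inputs**
- Threshold: 0.05 per test, from the text after the Study Aim Analysis items.
- Sidedness: not stated for the rank sum tests. The Power Analysis specifies a two-sided test for pain ("The sample size analysis is based on a two-sample, two-sided t-test with a significance level of 0.05 and 80% power"), and I assume the same here. Each test then has a 0.025 chance of a false result in the benefit direction.
- Arm size: 46 / 2 = 23 per arm, from the Power Analysis total before the attrition allowance. It only sets the size of the simulated rank sum tests. Whether 46 follows from the stated pain inputs is a separate question that does not bear on this point.
- Number of subscales: not in the documents. Assumed 8 for the SF-36 and 6 for the FSFI.
- Correlation between subscales: not in the documents. Assumed range 0 to 0.8, equal for all pairs.
- True effect: none on any subscale.
- Decision rule: any one significant subscale in the benefit direction counts as support. This is a reading of the plan, not its wording.

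**Step 1: independent subscales.** With k tests, P(at least one false benefit) = 1 − (1 − 0.025)^k = 1 − 0.975^k.
- k = 8 (SF-36): 1 − 0.8167 = 0.183
- k = 6 (FSFI): 1 − 0.8591 = 0.141

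**Step 2: correlated subscales.** Simulation of k equicorrelated rank sum tests, 23 per arm, 20,000 runs per setting, benefit direction only:

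| Correlation | k = 8 (SF-36) | k = 6 (FSFI) |
|---|---|---|
| 0 | 17.2% | 13.1% |
| 0.3 | 14.5% | 11.9% |
| 0.5 | 12.5% | 10.4% |
| 0.7 | 9.7% | 8.3% |
| 0.8 | 8.2% | 7.0% |

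The simulated values at correlation 0 sit slightly below the formula (18.3% and 14.1%).

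**Step 3: comparison with nominal.** Across both steps the range is 7.0% to 18.3%. Divided by 2.5%, that is 2.8 to 7.3, or roughly 3 to 7 times nominal.

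**Step 4: sensitivity to the assumed counts.** For 4 and 10 independent subscales the formula gives 1 − 0.975^4 = 9.6% and 1 − 0.975^10 = 22.4%.

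**Step 5: with one deciding score.** k = 1 gives 2.5% in the benefit direction for each instrument.

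**The case against.** The strongest reply is that the plan never says one significant subscale confirms a hypothesis. The 0.05 sentence defines when an individual analysis is significant and goes no further. That is correct, and it is why the error rates are conditional: the documented defect is the missing rule, and the rates describe one way of filling the gap.

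A second reply is that these are secondary goals in a 52-patient, one-facility trial whose stated purpose includes justifying a larger one. That also stands, and it limits the weight of the point. It does not remove it: the plan presents both goals as hypotheses with a significance threshold, and uses exploratory language only for the additional longitudinal analyses.

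A third reply is that the plan does not say it will test every subscale. True, but items 2 and 3 use plurals and name no subset, so testing all of them is the natural reading.

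A reader might infer something stronger: that a false significant benefit is likely. The documents do not support this. Counting false significance in either direction, 8 and 6 independent tests give 1 − 0.95^8 = 34% and 1 − 0.95^6 = 26%, but about half of that is false harm, which would not support either hypothesis. Pooling the two instruments raises the figure further, but each hypothesis concerns one instrument. Independence is also the least plausible case for subscales of one questionnaire.

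**Conclusion.** The point holds as a gap in specification. Each secondary hypothesis is tested through several subscales at an unadjusted 0.05, and nothing in the plan decides the hypothesis when they disagree. That much follows from the text alone.

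The size is conditional. With any-one-significant as the working rule, no true effect, 6 to 8 subscales and correlations of 0 to 0.8, the chance of a false benefit is about 7-18% per instrument instead of 2.5%. This is a material inflation, but a false benefit remains the less probable outcome in every case considered. The counts and correlations are assumptions that the documents cannot confirm. The primary pain analysis is untouched, so this is a desirable improvement, not a threat to the trial's main conclusion.

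**What to change.** Amend Study Aim Analysis, items 2 and 3, before unblinding:
- For each instrument, name one score whose change from baseline to 12 weeks is the sole 0.05 test of that hypothesis. It may be an overall or summary score or, if none is suitable, one named lead subscale. The documents do not say which overall scores are available, so the choice belongs to the investigators.
- State that the remaining subscales will be reported as between-arm differences with 95% confidence intervals and without significance claims.
- Limit the sentence applying 0.05 to all analyses so that it no longer covers those subscales.

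The planned rank sum test can stay for the deciding score. The change takes a few sentences and needs no extra patients, visits or data. Its downside is that an apparent effect confined to a subscale other than the deciding score could be described but not called significant. A score chosen after the results are seen would not repair the problem.

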addition to documenting these in a daily journal, we will encourage them to call and report these events. Each follow-up visit will evaluate and address any adverse event. The principal and co-investigators will review all adverse events and immediately report new events to the IRB. Our study will use a data safety monitor for adverse events. This individual has clinical expertise with chronic pelvic pain and will be blinded to the treatment arms. Monitoring will include assessments at 25% and 50% subject enrollment. If the data indicates harm, as described above in study aim analysis, the trial will be prematurely discontinued.

CONSENT

The principle investigator and co-investigators will consent the subjects in a private examination room. We will give all information in a clear and understandable manner and address all questions to the subject's satisfaction. Further emphasis will be made on the optional nature of this study and future care of the subject will not be dependent on participation.

Subjects who meet inclusion and exclusion criteria will be invited to participate at which time the study purpose, procedures, and requirements will be communicated. If she is interested in participating, she will sign the consent form and return for the initial study visit. Randomization will be performed at that subsequent visit. If the patient is unsure, she may leave and sign the consent form at the subsequent visit if still interested.

REFERENCES

- 2. Sluka KA ad Walsh D: Transcutaneous nerve stimulation: basic science mechanisms and clinical effectiveness. J Pain 2003; 4:109-121
- 6. Rosenbaum T. Addressing anxiety in vivo in physiotherapy treatment of women with severe vaginismus: a clinical approach. J Sex Marital There 2011; 37(2): 89-93

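### A significance test is a weak trigger for excess dropout on stimulation at about 13 and 26 women; the monitor should see the dropout data whatever the p-value

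*Combined protocol and SAP*

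**What the plan says.** The interim paragraph, under Study Aim Analysis, sets the timing: "Two interim analyses are planned for this study, to be conducted at 25% recruitment and 50% recruitment". It gives the levels in the next sentence: "These analyses will be conducted using significance levels of 0.017 and 0.033, respectively". A stopping rule on visual analog pain follows. The paragraph ends by saying that dropout percentages are monitored too, with "a significantly higher percentage of electrical stimulation patients dropping out being considered a potential safety issue".

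Other parts of the plan bear on how that could be applied, but none mentions dropout:

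- Statistical Methods lists the tests: "Univariable comparisons between groups will be made using two sample t-tests, Wilcoxon rank sum tests, or Chi-square tests". Chi-square is the one that fits a percentage. Continuity correction is not mentioned.
- The paragraph just before the interim one gives a different level: "In all analyses, statistical significance will be determined by a p-value less than or equal to 0.05".
- Adverse Events and Data Safety Monitor says "Our study will use a data safety monitor for adverse events", and of the monitor: "This individual has clinical expertise with chronic pelvic pain and will be blinded to the treatment arms". The timing matches the interim looks: "Monitoring will include assessments at 25% and 50% subject enrollment".

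**The concern.** Women who stop using an intravaginal stimulator may be showing that they do not tolerate it, and the plan itself treats dropout as a possible safety signal. A woman who leaves may give no later pain score, so the pain stopping rule may not see her. At 13 or 26 women, a difference in percentages must be very large before it reaches significance. If significance is what turns an imbalance into a concern, a substantial excess on active treatment could be passed over, and a non-significant result could be taken as reassurance. The percentage also leaves out when women left and why, which is often the most informative part.

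**Working it through.** **Look sizes.** Power Analysis gives 46 as the minimum and 52 as the recruitment target, 26 per arm. With 10% attrition, 46 / 0.90 = 51.1, which rounds up to 52 for equal arms, so the target is reproduced. Then 0.25 × 52 = 13 and 0.50 × 52 = 26. I take look 1 as 6 vs 7 or 7 vs 6 and look 2 as 13 vs 13, with look 1 contained in look 2.

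**Assumptions not in the plan.** True dropout by arm (sham 10%, stimulation 30% to 60%); chi-square as the test; 0.017 and 0.033 as the levels; dropout status complete for every woman at each look.

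**What it takes to flag.** For a of n stimulation and b of m sham dropouts, with N = n + m, the uncorrected statistic is N[a(m − b) − b(n − a)]² / [(a + b)(N − a − b)nm].

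- 5/13 vs 1/13 (38% vs 8%): 26 × (60 − 8)² / (6 × 20 × 13 × 13) = 70,304 / 20,280 = 3.47. Two-sided p = 0.063, no flag at 0.033. One-sided p = 0.031, a flag. Two-sided Fisher p = 0.16, no flag.
- 6/13 vs 1/13: 26 × (72 − 7)² / (7 × 19 × 13 × 13) = 109,850 / 22,477 = 4.89. Two-sided p = 0.027, a flag.

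With one sham dropout at look 2, six of 13 on stimulation are thus needed two-sided and five one-sided.

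**Chance of a flag at either look.** Sum the product of binomial probabilities over all outcomes at look 1 and all later outcomes up to look 2. Count an outcome if p ≤ 0.017 at look 1 or p ≤ 0.033 at look 2, with the stimulation rate the higher. Ranges cover the two look-1 splits.

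| True dropout, stimulation vs sham | Uncorrected, two-sided | Uncorrected, one-sided | Corrected, two-sided | Corrected, one-sided |
|---|---|---|---|---|
| 30% vs 10% | 22% | 36-37% | 5% | 12% |
| 40% vs 10% | 40-41% | 56-57% | 15-16% | 28% |
| 50% vs 10% | about 60% | 74% | 33% | 49% |
| 60% vs 10% | 77-78% | 87-88% | 55% | 71% |

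Fisher's test at 40% vs 10% gives 20% two-sided and 28% one-sided.

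**The other level.** With 0.05 at both looks, uncorrected chi-square gives 24-27% two-sided and 41-46% one-sided at 30% vs 10%, and 46-48% and 63-66% at 40% vs 10%.

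**Incomplete follow-up.** The looks are set by recruitment and treatment lasts 12 weeks, so some women will be part-way through. Assume a constant hazard, with observed rate 1 − (1 − p)^f when a fraction f of follow-up has been seen. Look 2 alone, 40% vs 10%, uncorrected, at 0.033:

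- f = 1: 39.5% two-sided, 54.4% one-sided.
- f = 0.75 (observed 31.8% vs 7.6%): 31% and 47%.
- f = 0.5 (observed 22.5% vs 5.1%): 19% and 35%.

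**The case against.** The strongest reply is that the plan does not say what the calculation tests. Its wording names one trigger. It does not say that a smaller imbalance will be disregarded, and it monitors the percentage in any case. The pain rule in the same paragraph specifies statistical significance; the dropout sentence omits that adverb. The test, sidedness and level used above come from other sentences. This stands: the percentages describe a plausible reading, not a stated procedure. A reader might infer that excess dropout counts only if significant, or that it will be examined only at the two looks. The text says neither, though these looks are the only trial-level monitoring points it schedules.

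A reader might also infer that the rule misses a large excess more often than it catches it. That is not supported in general. The rule is directional, so a one-sided test is a natural reading; uncorrected and with full follow-up it flags 40% vs 10% somewhat more often than not, and 50% or 60% vs 10% in most trials.

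Other safeguards are real: daily recording of side effects, encouraged telephone reports, review at each visit, immediate reporting to the IRB, the safety monitor and the pain stopping rule. Harm that leads to withdrawal can surface through any of these.

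Finally, scant information at 13 and 26 women limits every method. An exact 95% interval for 5/13 vs 1/13 runs from about −4 to +60 points, so an interval does not make the comparison more sensitive. What the fix adds is the timing and reasons, and an end to treating non-significance as the dividing line.

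**Conclusion.** The point holds as a modest improvement to safety monitoring. If the dropout rule is a significance test, it is a weak signal at the planned looks: at 40% vs 10%, uncorrected and fully followed, it stays silent in about 59-60% of trials two-sided and 43-44% one-sided. At 30% vs 10% it stays silent more often than not under every variant shown. Larger excesses are caught more often, and the answer depends on choices the plan leaves open. All of this rests on assumed dropout rates; the plan's only attrition figure is an overall 10% allowance. The consequence is limited, because dropout is one signal among several and a significant excess is described only as a potential safety issue. It might be inferred that the monitor has to be unblinded for the signal to be usable. The documents do not support that: a table by coded arm shows an imbalance and keeps the blinding that the plan specifies.

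**What to change.** Reword the dropout sentence so that significance is not the condition for concern. At both planned looks, give the safety monitor one table of dropout counts, timing and reasons by coded arm, to be judged together with the adverse events. State that a non-significant difference is not evidence of safety. A difference with an exact confidence interval may be added but is optional. Access to the arm code is a separate decision with a cost to blinding and is not part of this change.

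The cost is a few sentences and one table per look, at looks already planned, with no change to sample size, visits or efficacy analysis. The small downside is that judgement replaces a fixed trigger.
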